## **STUDY DESIGN**

### **1. Phase**

Not applicable

#### ***2.1 Design of tDCS-Only Study***

This is a sham-controlled, full cross-over study design. All subjects with PPA will participate in ten 20-minute tDCS stimulation sessions over the course of 2 weeks using 1.5 mA current. A battery of language tasks will be administered before stimulation sessions, after the 10 sessions, and again at 6 and 12 weeks after the stimulation sessions. The 12-week follow up session will serve as the "baseline" session for the following stimulation sessions. All subjects will also participate in ten 20-minute sham stimulation sessions over the course of 2 weeks. During sham tDCS, a 1.5 mA current will be delivered for approximately 30 seconds at the beginning of the sham session before being extinguished over the course of seconds. Participants will be randomly assigned to receive sham or tDCS stimulation first.

For example, a subject who is assigned to sham stimulation sessions first will first undergo baseline language testing. Then the subject will participate in ten 20-minute sham stimulation sessions over the course of 2 weeks. The subject will go through follow up language testing after the 10th sham stimulation sessions as well as 6 and 12 weeks following the sham stimulation sessions. The 12 week follow up session will serve as the "baseline" for the tDCS stimulation sessions, after which the subject will participate in ten 20-minute tDCS stimulation sessions over the course of 2 weeks, using 1.5 mA current.

#### ***2.2 Design for HD-tDCS+CILT Sub-study***

For the HD-tDCS+CILT study, we will use the same sham-controlled, full cross-over design described above, with two exceptions: 1) We will conduct two baseline testing sessions on separate days prior to the start of the 10-day tDCS block, to facilitate screening for CILT and to ensure a stable estimate of language performance at baseline; 2) After the completion of the final 12-week follow-up visit, participants will have the option to undergo an additional 10-day round of “booster” HD-tDCS/sham+CILT. This booster will be open to any patients as an optional incentive for patients whose completion of the study coincided with perceived benefits from the combined therapy. The booster will involve the same time-course of language assessments, HD-tDCS+CILT sessions, and follow-up testing out to 12 weeks after the final HD-tDCS session. This optional third arm of the protocol will thus be identical to the real HD-tDCS arm in all ways (i.e., assessment schedule, subject compensation, tDCS parameters etc.) except that participants may opt in or out as they see fit. In other words, all participants are expected to complete the first two arms of HD-tDCS/sham stimulation; then, those who have completed all the scheduled study visits may choose to undergo a third round, during which we will continue to collect the same data that we have collected throughout the rest of the study.

## ***2.2 Design for tDCS with svPPA Sub-study***

For the tDCS with svPPA sub-study, we will also conduct a sham-controlled, full cross-over design. Participants will undergo a battery of cognitive and language testing before treatment. Participants will be pseudo-randomly assigned to two groups, A & B. Group A will receive sham stimulation first, while group B will receive active stimulation first. Groups will be stratified by severity of global cognitive impairment as indexed by performance on the Montreal Cognitive Assessment.

All subjects will participate in ten 20 minute tDCS stimulation sessions over the course of 2 weeks using 2 mA current. The battery of tasks will be administered before stimulation sessions, after the 10 sessions, and again at 12 weeks after the stimulation sessions. The 12-week follow up session will serve as the "baseline" session for the following stimulation sessions. All subjects will also participate in ten 20-minute sham stimulation sessions over the course of 2 weeks. During sham tDCS, a 2 mA current will be delivered for approximately 30 seconds at the beginning of the sham session before being extinguished over the course of seconds. Participants will be randomly assigned to receive sham or tDCS stimulation first. After the second treatment/sham period, the cognitive/language tasks will be administered again, and then additionally at 6 and 12 week follow-up sessions.

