Half of subjects will undergo 10 sessions of sham stimulation first and will then undergo 10 sessions of real tDCS stimulation. Half of subjects will undergo 10 sessions of real tDCS stimulation first and will then undergo 10 sessions of sham stimulation. A complete language assessment will be performed before stimulation sessions, after the 10th stimulation session, and 12 weeks and 6 months ( $\pm$  1 week) after the completion of stimulation sessions. Real tDCS stimulation will be administered using the Soterix 1x1 using a current of 2 mA. The cathodal current will be split across two electrodes (5cm^2) positioned over the left and right temporal regions respectively. The anodal electrode (5x7cm) will be placed over the forehead. During sham stimulation, a 2 mA current will be delivered for approximately 10 seconds at the beginning of the sham condition before being extinguished over the course of seconds. After the first 10 minutes of stimulation, in both real and sham conditions, participants will begin the behavioral treatment, which will continue for 45 minutes; therefore there will be 20 minutes of concurrent tDCS and behavioral therapy.

Prior to initiating treatment, we will craft an individualized training lexicon for each patient. This training vocabulary contains familiar people, household items, foods, activities, cloths, and hygiene implements. Target words are represented by photographs of the patient's own items. We will employ several item-level controls to examine treatment generalization. The first will test the impact of personal familiarity by asking patients to name and generate features for canonical rather than personal photographs. The second condition will evaluate within-category generalization by asking patients to name and generate features for their own untrained items. The final item-level comparison will examine generalization of naming accuracy to untrained

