## **2. Statistical Analysis**

Data from each subject will be analyzed using a within-subject design in which change in performance from the baseline testing session to the post-therapy (0, 6, 12 weeks post tDCS) will be compared using t-tests, ANOVAs and other univariate statistics. As it is most relevant to real-world behavior, elicited speech production will serve as the primary endpoint. Depending on our ability to recruit a reasonable sample, group analyses will be also be performed. Finally, we note that high quality imaging will be available for the majority of subjects. Note that we are not proposing to obtain imaging under the auspices of the present study; this data will be available from [name] previously cited protocol. We will perform exploratory analyses in which we attempt to determine if specific imaging parameters (e.g., cortical thickness, degree of atrophy) predict response to tDCS.

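### svPPA sub-study: the analysis names no sequence or period term, nor the MoCA factor used for assignment, so a period effect would stay in the error term of a plain paired comparison; the allocation method also needs one description.

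*Combined protocol and SAP*

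**What the plan says.** Study Design, 2.2 Design for tDCS with svPPA Sub-study, sets up a two-period cross-over: "For the tDCS with svPPA sub-study, we will also conduct a sham-controlled, full cross-over design". On assignment it says "Participants will be pseudo-randomly assigned to two groups, A & B", where A is sham first and B is active first, and then "Groups will be stratified by severity of global cognitive impairment as indexed by performance on the Montreal Cognitive Assessment". Its next paragraph says "Participants will be randomly assigned to receive sham or tDCS stimulation first". Study Procedures, 1.3, adds equal halves: "Half of subjects will undergo 10 sessions of sham stimulation first and will then undergo 10 sessions of real tDCS stimulation", with the other half in the reverse order. No MoCA cut-points, number of strata, generator, list holder or concealment step is given. The same design section makes the 12-week follow-up of the first block the baseline of the second.

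Study Procedures, 2. Statistical Analysis, is shared by all the studies in the protocol. It begins "Data from each subject will be analyzed using a within-subject design in which change in performance from the baseline testing session" and says that change to the post-therapy visits "will be compared using t-tests, ANOVAs and other univariate statistics". It then adds "Depending on our ability to recruit a reasonable sample, group analyses will be also be performed". The short section on primary outcome variables names the same families of test. Neither section mentions sequence, period or MoCA.

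**The concern.** The design fixes two things that the analysis does not use: the order of treatment and the MoCA stratum.

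Order matters because the Background describes PPA as slowly progressive. Block 2 begins from the block-1 12-week visit, so participants enter it with more advanced disease and with practice on the same tests. Change over block 2 may therefore differ from change over block 1 whatever the stimulation. With equal halves in each order, such a shift averages out of the active-minus-sham mean. In a plain paired t-test, however, it adds a positive amount to one half's differences and a negative amount to the other half's. The test treats that spread as noise. The interval is then too wide and power is lost in a sub-study that is likely to be small.

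MoCA is a lesser matter. It is collected and used for assignment, so the analysis should say whether it enters the model. The two words for allocation raise a separate question of clarity.

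**Working it through.** **Inputs.** From the documents: two-period cross-over, half in each order, within-subject change as the outcome. The documents give no N, SD, effect size, alpha or power for svPPA, so there is no planned figure to reproduce. Assumptions: N = 20 (the roughly 10 a year for 2 years stated for the other two studies), 10 per order, two-sided 5%, and a mean active-minus-sham difference of 0.6 SD. SD here means that of the block-1 minus block-2 change, set to 1.

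**Model.** Let D be block-1 change minus block-2 change, s = +1 for active first and −1 for sham first, p the period shift, τ the treatment effect and e the error:

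D = p + τ·s + e

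Regressing D on s puts p in the intercept, and the coefficient of s estimates τ. The paired t-test uses s·D = τ + p·s + s·e, so p·s goes into the residual.

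**Size of the period problem.** With equal orders, the expected residual variance of the paired test is 1 + p²·N/(N−1).

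- p = 0.5: √(1 + 0.25 × 20/19) = √1.263 = 1.124. After allowing for critical values of 2.093 (19 df) and 2.101 (18 df), the ratio is 1.124 × 2.093/2.101 = 1.12, about 12% too wide.
- p = 1: √(1 + 20/19) = √2.053 = 1.433, about 43% too wide.
- p = 0: the sequence term costs 2.101/2.093, under 0.5% in width.

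Power with the sequence term: non-centrality 0.6 × √20 = 2.68 on 18 df, giving 72% whatever p is. By simulation, the paired test has power of 63% at p = 0.5 and about 40% at p = 1.

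*Cross-check on another scale.* Give each change score a residual SD of 1, so the block difference has SD √2. A shift of one change-score SD is then 1/√2 = 0.707 on the scale above, and the formula gives √(1 + 0.5 × 20/19) = 1.235. A separate simulation gave a mean SE of 0.392 against a true SD of 0.317, a ratio of 1.237. With a sequence term the SE was 0.317.

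**Size of the MoCA problem.** Take two equal strata balanced across orders, with correlation r between stratum and D. The expected residual variance is 1 − r² + r²·N/(N−2) without the stratum (18 df) and 1 − r² with it (17 df, critical value 2.110).

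| r | width without MoCA / width with MoCA | excess |
|---|---|---|
| 0 | 2.101/2.110 = 0.996 | none |
| 0.2 | √(1.0044/0.96) × 0.996 = 1.019 | about 2% |
| 0.3 | √(1.010/0.91) × 0.996 = 1.049 | about 5% |
| 0.5 | √(1.0278/0.75) × 0.996 = 1.166 | about 17% |

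With two equal strata, r means that the strata differ by 2r SD in D. So r = 0.3 is already a difference of 0.6 SD, as large as the treatment effect assumed. If MoCA affects level, or rate of change equally in both blocks, then r = 0 and it drops out. In simulation at N = 20 that case gave a paired-test SE of 0.315 against a true SD of 0.315.

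**Smaller N.** At N = 8, p = 0.5 gives √(1 + 0.25 × 8/7) × 2.365/2.447 = 1.10, still about 10% too wide. With r = 0, adding MoCA to the sequence model takes power from about 30% (6 df) to 28% (5 df).

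**Allocation.** With past assignments known and two strata, the next order can be guessed correctly about 75% of the time with blocks of 2 and 68% with blocks of 4, against 50% for simple randomisation. Strict alternation is fully predictable after the first assignment. The documents do not say which scheme applies.

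**The case against.** *The plan does not exclude the right model.* An ANOVA can carry sequence, period and stratum factors, and group analyses are conditional on recruitment. This stands in part: the plan does not commit to an unadjusted test. It does not commit to an adjusted one either, and a paired t-test is a natural reading of the text.

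*The error is conservative.* A period shift left in the residual widens the interval; it does not produce false positives when the orders are balanced. This stands, and it makes the matter one of lost power.

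*MoCA cancels.* A reader might infer that stratifying on MoCA and then leaving it out must make the intervals too wide. That is the familiar result for parallel groups with a prognostic stratum. Here each participant is their own control, and nothing in the documents says that severity changes the difference between blocks. The inference fails as a general claim and holds only under such a relation. A between-group comparison of first blocks would be exposed, but the plan does not propose one.

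*Pseudo-random may be harmless.* A reader might also infer that staff place participants by hand, so that the order is predictable and decliners can be steered to one sequence. The documents do not support this. The word may simply mean computer-generated or constrained randomisation, and the later sentence matches the one in the tDCS-Only design section, so it may be carried-over text. The Procedures place MoCA testing after consent, so the stratum itself comes from post-consent testing. Missing detail leaves predictability open without showing it.

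**Conclusion.** The concern holds as a gap in the specified model. No stated term removes a period effect that the design makes plausible. Under the assumptions of N = 20, equal orders and a 0.6 SD effect, a plain paired test costs about 9 percentage points of power at a shift of 0.5 SD and about 32 at 1 SD. There is no material cost if the shift is zero. The size of any real shift is unknown, and differential carry-over was not examined.

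For MoCA the gain is conditional and usually smaller, and at very small N the term can lose a little precision. The mixed wording on allocation calls for clarification; neither predictability nor bias has been demonstrated. Overall this is an inexpensive improvement and not a threat to validity.

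**What to change.** In Study Procedures, 2. Statistical Analysis, add for svPPA that the group comparison regresses the block-1 minus block-2 change on sequence and on the MoCA stratum (or baseline MoCA score). State that the sequence coefficient carries the active-versus-sham contrast and the intercept carries the period effect. State in advance that if the achieved N is very small, the primary model keeps sequence only and the MoCA-adjusted model becomes a sensitivity analysis.

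In Study Design, 2.2 Design for tDCS with svPPA Sub-study, replace the two descriptions with one: a computer-generated list within MoCA strata, with the cut-points stated and the order revealed only after baseline testing. Naming who holds the list and keeping any block size from enrolling staff would limit guessing.

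The cost is a few sentences and one or two degrees of freedom. MoCA is already collected. At N = 20 the loss is negligible when neither term is needed; at N = 8 the MoCA term costs about 2 percentage points of power.

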## ***3.1 Study Duration of tDCS-Only Study***

We expect this project to last for approximately 2 years. We expect to enroll approximately 10 subjects annually. Duration of subjects' participation in the study will be approximately 8-10 months.

### **3.2 Study Duration of HD-tDCS+CILT Sub-study**

We expect this project to last for approximately 2 years. We expect to enroll approximately 10 subjects annually. Duration of subjects' participation in the study will be approximately 8-16 months, depending on the participants' choice to undergo booster therapy or not.

## **DRUGS OR DEVICES**

We will be using commercially available tDCS and HD-tDCS devices manufactured by Magstim, the Magstim Eldith 1 Channel DC Stimulator Plus. The unit is powered by rechargeable batteries and includes a microprocessor controlled unipolar and bipolar constant source for anodal and cathodal stimulation. We note that this apparatus is currently being employed in an IRB approved protocol (#809185) in which more than 200 tDCS sessions have been conducted without significant adverse effects. The unit is not FDA approved for any clinical purposes. The tDCS unit will be used in a locked laboratory in HUP in which the lab's TMS apparatus is currently situated. Only the PI and other members of his research team have keys to this laboratory. When not in use, the unit will be enclosed in a special, dedicated storage container that will be marked with a statement that the enclosed unit is not to be used for clinical purposes. During these times the unit will be housed in the PIs personal space located in the University of Pennsylvania School of Medicine and stored in a locked cabinet to which only the PI and his staff have access. Additionally, the unit itself will be clearly marked with a statement indicating that it is an investigational instrument only.

## **STUDY PROCEDURES**

### **1.1 Procedures for tDCS-Only Study**

After obtaining informed consent, a baseline language assessment will be performed for all subjects, regardless of whether they will be assigned to sham or real tDCS stimulation first. Depending on the subject, this assessment is expected to take 1-2 hours. Performance will be audio-recorded. The assessment will include the following measures: - Confrontation Naming: we will administer the Boston Naming Test, a commonly used measure of picture naming/word retrieval in which a line drawing is presented and subjects are asked to name the object. - Pyramid and Palm trees: a well-standardized test in which subjects see 3 pictures or words on a page and are asked which two "go together"; for example on one page, the pictures include a drawing of a glove, hand and foot. -Grammatical Comprehension (L-TROG): a standardized test in which subjects are asked to judge whether an auditorily presented sentence is correct. - Category fluency: a series of tasks in which subjects are asked to generate as many words as possible in one minute that are

members of a specific category; semantic categories will include tools, animals, and vegetables. Subjects will also be asked to generate words starting with the letters F, A and S. - Repetition, Reading and Writing (single words) will be assessed using the materials developed by the NACC-FTD consortium; subjects are asked to read, write and repeat a series of words controlled for variables known to influence performance such as length, part of speech (noun, verb), imageability (desk vs. fate), age of acquisition, etc. - Elicited Speech Production: Speech samples will be elicited from subjects by presenting a picture book (e.g., Frog story) or scene to be described (Cookie Theft picture from the Boston Diagnostic Aphasia Examination) and asking subjects to describe what they see. Speech production will be scored off-line with respect to fluency (words/minute), grammatically well-formed sentences, mean length of utterance, nouns/100 words, verbs/100 words, phonemic errors, and phonetic errors. Half of subjects will undergo 10 sessions of sham stimulation first and will then undergo 10 sessions of real tDCS stimulation. Half of subjects will undergo 10 sessions of real tDCS stimulation first and will then undergo 10 sessions of sham stimulation. A complete language assessment will be performed before stimulation sessions, after the 10th stimulation session, and 6 and 12 weeks ( $\pm$  1 week) after the completion of stimulation sessions. Real tDCS stimulation will be administered using our standard apparatus (Magstim Eldith with 5x5 cm electrodes) using a current of 1.5 mA. (As a frame of reference, we routinely use 2 mA current in other studies.) The anode will be placed over the left fronto-temporal region of the brain and the cathode over the left occipito-parietal region. During sham stimulation, a 1.5 mA current will be delivered for approximately 10 seconds at the beginning of the sham condition before being extinguished over the course of seconds. As there is some evidence that engaging in the activity that one wishes to enhance while undergoing tDCS improves outcome, all subjects will be shown a children's picture book (e.g., the illustrated version of Cinderella) during the 20 minute period of stimulation and asked to narrate the story, regardless of whether they are in real tDCS stimulation or sham stimulation. Participants assigned to receive sham treatment first will cross over to real tDCS treatment after the 12-week follow up session. Each participant will then receive real tDCS stimulation for 10 sessions over the course of two weeks. The stimulation parameters and testing during treatment will be identical to the previous stimulation sessions, except this time participants will receive real tDCS stimulation instead of sham stimulation. Participants assigned to receive real tDCS stimulation first will cross over to sham stimulation after the 12-week follow up session. Each participant will then receive sham stimulation for 10 sessions over the course of two weeks. The stimulation parameters and language testing during treatment will be identical to the previous stimulation sessions, except this time participants will receive sham stimulation instead of real tDCS

stimulation.

Safety and tolerability of the treatment will be assessed in several manners. First, the inclusion/exclusion screening form will be administered both at the initial intake session, as well as at the first session of each 2-week stimulation block. Second, subjects will be queried about new symptoms or adverse effects prior to stimulation on all days when stimulation will be given; should subjects have any concerns, tDCS will not be performed and language will be assessed with fluency tests, naming and a speech sample will be elicited. Third, in the absence of symptoms, language will be assessed at the end of one week of treatment with picture naming, fluency measures and a speech sample will be elicited. Should performance be significantly worse than prior to initiation of treatment, the study will be discontinued; in this event, subjects will be followed on a weekly basis for 4 weeks or until performance returns to baseline (whichever comes first). We propose to use a "significant" change in performance as a cut-off because performance in this condition in the absence of any intervention is quite variable.

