## ***8. Real time safety monitoring***

Subjects and equipment will be monitored at all times during tDCS and HD-tDCS studies by a trained member of the research personnel list approved to be on the protocol. During the first stimulation session, participants will come to the lab here at the University of Pennsylvania and a physician will be on call within 5 minutes of the testing room. As long as the subject does not experience any adverse events during that first stimulation session and the research staff have no

reservations, then in all subsequent stimulation sessions, whether conducted in the patient's home or in the laboratory here at the University of Pennsylvania, one of the physicians associated with the study will respond to any concerns within 24 hours. Additionally, the trained personnel administering stimulation will look for any evidence of discomfort in the participant and will verbally inquire about any discomfort. The investigator or trained personnel will also observe and monitor the equipment. In the unlikely event that either the subject or the person administering tDCS or HD-tDCS has significant concerns and the PI cannot be immediately contacted, the subject would be escorted to the Emergency Room.

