Visit 14	Visits 15-22	Visit 23		Visit 24		Visit 25
Post-HD-tDCS/2nd baseline language testing; Begin HD-tDCS+CI LT	HD-tDCS+CI LT	HD-tDCS+CI LT; Post-tDCS language testing	(6 week break)	Post-HD-tDCS language testing	(6 week break)	Post-HD-tDCS language testing

The HD-tDCS stimulation parameters will be similar to the tDCS-only study. 0.5 cm^2 cup electrodes filled with conductive gel will be placed so that the one electrode (anode) is placed over the targeted region of cortex and electrodes of opposite polarity (cathode) are arranged in four equidistant points around the anode to form an imaginary square. Stimulation will not exceed 1.5 mA in intensity and will not exceed 20 minutes in duration per session. As above, 30-second ramp-up and ramp down periods will be employed before and after stimulation for both real and sham sessions. Afterward CI LT, the tDCS electrodes and elastic band or cap will be removed and the subjects' head will be wiped clean. PPA is typically associated with cortical atrophy in the left hemisphere, but the exact location depends on the variant of the disorder. Patients with semantic-variant PPA tend to have atrophy concentrated in the left temporal lobe, whereas patients with nonfluent forms of the disorder tend to have atrophy more concentrated in the left frontal lobe. We will use Soterix tDCS-Explore™ (Soterix Medical Inc., New York, NY) modeling software to place the anode and the cathode over regions that best concentrate the delivery of current to the relevant portion of the left hemisphere. Similar modeling software will be used to determine the exact location of stimulation during HD-tDCS. Based on modeling studies, the current flow during HD-tDCS stays focal, instead of diffusing widely throughout the brain. Exact electrode placement for scalp electrodes presents no additional safety concerns relative to our previous placement of electrodes.

Half of subjects will undergo 10 sessions of sham stimulation first and will then undergo 10 sessions of real tDCS stimulation. Half of subjects will undergo 10 sessions of real tDCS stimulation first and will then undergo 10 sessions of sham stimulation. A complete language assessment will be performed before stimulation sessions, after the 10th stimulation session, and 6 and 12 weeks ( $\pm 1$  week) after the completion of stimulation sessions.

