
tDCS+CILT session will be from a more difficult category (e.g., moving from high to low frequency objects, or from low frequency objects to high frequency actions, and so on). Sessions will be audio-recorded and performance will be scored across cuing levels. The CILT sessions will last up to 1.5 hours each, with HD-tDCS terminating after 20 minutes of stimulation.

Safety and tolerability of the treatment will be assessed in several manners. First, the inclusion/exclusion screening form will be administered both at the initial intake session, as well as at the first session of each 2-week stimulation block. Second, subjects will be queried about new symptoms or adverse effects prior to stimulation on all days when stimulation will be given; should subjects have any concerns, HD-tDCS will not be performed and language will be assessed with fluency tests, naming and a speech sample will be elicited. Third, language will be assessed immediately following the 10th HD-tDCS+CILT session with the WAB, the 60-item image set, and the patient/caregiver CAL. Should there be a clinically significant decrease in performance on the WAB (a reduction in score of **5 or more points**) compared to the participant's WAB score on day 1 of the treatment, the participant's visits will be discontinued; in this event, subjects will be followed on a weekly basis for 4 weeks or until performance returns to baseline (whichever comes first). We propose to use a "significant" change in performance as a cut-off because performance in this condition in the absence of any intervention is quite variable.

After the final visit of the HD-tDCS+CILT sub-study (i.e., the last 12-week follow-up), participants will have the option to participate in one additional round of 10 HD-tDCS+CILT sessions, to be scheduled no earlier than 3 months after study completion and no later than 6 months following study completion.

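### No adverse-effect query is scheduled between session 10 of a block and the next stimulation day, and none after the final block, although follow-up visits continue

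*Combined protocol and SAP*

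**What the plan says.** Study Procedures 1.1 (tDCS-Only) lists three safety and tolerability measures:

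- a screening form at intake "as well as at the first session of each 2-week stimulation block";
- a symptom query: "subjects will be queried about new symptoms or adverse effects prior to stimulation on all days when stimulation will be given";
- a language check after one week of treatment.

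Section 1.3 (svPPA) has the same list. Section 1.2 (HD-tDCS+CILT) keeps the first two and moves the third to the end of the block: language is tested after the tenth "session with the WAB, the 60-item image set, and the patient/caregiver CAL". Those are language and communication measures, not questions about symptoms.

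There is a second inquiry. Under Real time safety monitoring (section 8 of the study population chapter), staff administering stimulation "will look for any evidence of discomfort in the participant and will verbally inquire about any discomfort". The chapter on resources for human research protection repeats this.

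The later visits are described by their testing content. In section 1.1: "A complete language assessment will be performed before stimulation sessions, after the 10th stimulation session, and 6 and 12 weeks" after stimulation ends. In the HD-tDCS+CILT schedule, Visit 14 is "Post-HD-tDCS/2nd baseline language testing; Begin HD-tDCS+CI LT", so the 12-week visit of block 1 is also the first stimulation day of block 2. In the other two parts the 12-week visit is the baseline for block 2.

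Data and Safety Monitoring (Risk/Benefit Assessment, section 4) gives the principal investigator the task of monitoring for adverse effects. It names no form, schedule or end date.

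**The concern.** A question asked before a session picks up what has happened since the previous session. Nothing in the written schedule does the same for the period after session 10, which is when a delayed or cumulative effect of a full ten-session course would appear. Participants return during that period, but the visits are specified without a symptom question.

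Two things are at stake. First, delayed effects after the final block reach the record only if someone volunteers them or a member of staff happens to ask. Volunteering is a weak route here, because the protocol itself expects some participants to have trouble understanding what is explained to them. The protocol also cites only one PPA patient treated with tDCS and describes those data as very limited, so this study's own safety record matters. Second, an effect that began after block 1 may first be elicited on day 1 of block 2. No rule for recording onset is given, so it could be counted against the wrong block.

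**Working it through.** No rate, power or error probability is involved. The check places every described inquiry on the visit schedule.

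**1. Reproduce the plan's visit count.** Section 1.2 states nine assessment visits. The HD-tDCS+CILT table gives language testing at Visits 1, 2, 3, 12, 13, 14, 23, 24 and 25, which is nine and agrees. Stimulation days are Visits 3–12 (10) and 14–23 (10), so 10 + 10 = 20 of 25 visits carry the pre-stimulation query.

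**2. What the query covers within a block.** The query before session k covers the interval since session k − 1. Ten queries therefore cover the intervals after sessions 1 to 9, and the interval after session 10 is left open. The discomfort inquiry by staff giving stimulation covers session 10 while it is running, but not the days and weeks afterwards.

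**3. Assessments at or after session 10 in HD-tDCS+CILT.**

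| Visit | Timing | Scheduled query about the time after session 10? |
|---|---|---|
| 12 | session 10, block 1 | no; query only before that session |
| 13 | 6 weeks | no |
| 14 | 12 weeks, and first session of block 2 | yes |
| 23 | session 10, block 2 | no; query only before that session |
| 24 | 6 weeks | no |
| 25 | 12 weeks | no |

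One of six carries such a query; after the final block it is none of three. In tDCS-Only the pattern is the same, except that the documents do not say whether the first session of block 2 falls on the day of the 12-week visit. Either way the query and the repeat screening form come at that session.

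**4. Length of the gap.**

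- After block 1, tDCS-Only and HD-tDCS+CILT: about 12 weeks. With the 1-week window on the visit, 12 − 1 = 11 to 12 + 1 = 13 weeks.
- After the final block, same two parts: no scheduled query for the remaining follow-up of about 12 weeks (11 to 13).
- svPPA: the Study Design section puts the visits after the second period at 6 and 12 weeks. Procedures 1.3 gives 12 weeks and 6 months. The period without a query is 12 weeks or 6 months, depending on which text is followed.
- HD booster: section 1.2 allows it from 3 to 6 months after study completion. A participant who takes it is queried again about 12 weeks plus 3 to 6 months after session 10 of block 2. The booster's own 12-week follow-up then has the same gap.

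**5. By treatment order.** Half of participants are allocated to each order.

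| Order | Later query after active block | Later query after sham block |
|---|---|---|
| active first | yes, block 2 day 1 | no |
| sham first | no | yes, block 2 day 1 |

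Pooled over the two orders, each condition has a later query in half of participants. The gap follows the period, not the treatment. With about 10 enrolled a year for 2 years (10 × 2 = 20) in tDCS-Only or in HD-tDCS+CILT, about 10 per part would have no scheduled query after their last planned active session, assuming equal allocation, no dropout and no booster. The other 10 would have none after their last sham session.

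**The case against.** The strongest case on the other side is that safety information does not stop at the pre-stimulation query. Staff ask about discomfort at sessions, session 10 included, and the effect the protocol calls most common is itching and mild burning under the electrode, which is what that inquiry would catch. HD Visit 14 is a 12-week visit with a query. Block 2 day 1 brings a query and a repeat screening form in every part. Language decline is treated as a safety signal, and language is retested at every follow-up visit. The principal investigator monitors for adverse effects with no stated end date. The protocol identifies no delayed effect of tDCS, and Statistical Analysis plans no comparison of tolerability.

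All of this is correct, and it limits the point. It rules out three stronger conclusions that a reader might draw:

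- *That adverse effects are asked about only before stimulation.* The in-session inquiry contradicts this.
- *That effects after the last block are never collected.* General monitoring is assigned; what is missing is a method and a schedule.
- *That the gap biases active against sham.* It falls equally on both conditions when half are allocated to each order.

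What the objection does not do is supply a scheduled symptom question after session 10 of the final block. The in-session inquiry ends with the session, language scores are not symptoms, and the extra weekly follow-up starts only if language performance worsens.

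**Conclusion.** The point holds in a limited form. Followed as written, the plan has no scheduled adverse-effect query from session 10 of block 1 until block 2 day 1, about 12 weeks later, and none after session 10 of the final block for the remaining 12 weeks or so (12 weeks or 6 months in svPPA), apart from HD participants who take the booster. The consequence is reduced capture of delayed effects, and uncertain attribution of block-1 effects first reported on block 2 day 1.

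This assumes that the written visit content is complete. Staff may well ask in practice, but the documents do not require it. The absence of a differential effect assumes roughly equal allocation to the two orders and similar completion of both. No planned efficacy analysis is affected. It is an inexpensive improvement to safety collection and does not invalidate the design.

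**What to change.** In the safety paragraphs of Study Procedures 1.1, 1.2 and 1.3, add the existing query about symptoms and adverse effects at the assessment after session 10 and at every scheduled follow-up visit, in both blocks and in the HD booster. Word and administer it identically for real and sham. Record the onset date of each event, and report adverse effects by the block in which they began.

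Reconcile the svPPA follow-up times between Study Design and Procedures 1.3, so that it is clear which visits carry the query.

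The cost is a few extra minutes at visits already scheduled, using a question set already in use. No visits or staff are added.
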